3.4. INVESTIGATIONAL PRODUCT

The IP, PHV01, was manufactured under GMP conditions by National Resilience (formerly Ology Bioservices) in Alachua, FL for PHV. Subjects will receive a 1 mL IM injection of PHV01 or placebo, according to the randomization plan. Lactated Ringer's solution USP will be used as the diluent and placebo. Sites will source the Lactated Ringer's solution USP from their pharmacy and will only utilize solution that is approved for parenteral use in humans, noting lot number and certificate of testing. See the Pharmacy Manual for details on the specific lot of IP to be used, the vial label, and methods for preparing dosing materials for administration to study participants.

3.4.1. Investigational Product Storage and Preparation

PHV01 Drug Product (DP) is provided as a sterile, frozen, preservative-free liquid for IM injection containing $\geq 1 \times 10^7$ pfu of rVSV Δ G-MARV-GP, pH 6.8-7.8. No novel excipients or components of animal or human origin are used in the manufacture of the Drug Substance (DS) or DP.

Each single-dose vial contains 0.9 mL of IP. In addition to the virus, PHV01 contains 2.5 mg/mL recombinant human albumin (rHA) and 10 mM Tris at pH 7.2. No preservative is included in these single-use vials. The composition of PHV01 DP is shown below.

Table 4. PHV01 Drug Product Composition

Component	Purpose	Grade	Concentration	
rVSV∆G-MARV-GP virus (PHV01)	Active ingredient	GMP	$\geq 1 \times 10^7 \text{pfu/mL}$	
Recombinant human albumin	Stabilizer of virus	USP-NF	2.5 mg/mL (0.25%)	
Tris pH 7.2	Buffer (pH control)	GMP, USP/EP	10 mM	

The DP is a clear to opalescent, colorless solution, free from visible particulates. Residual host cell DNA is ≤ 10 ng/mL and endotoxin < 20 EU/mL. The vaccine is supplied in a 2-mL glass vial containing an extractable volume of 0.9 mL. For use in clinical trials, dilution to specified dose (potency, pfu/mL) may be required. NOTE: the DP concentration (titer) of virus varies from lot to lot. Refer to the Pharmacy Manual for the composition of the lot to be used in the clinical trial.

The vaccine must be stored in the original container/vial in the freezer at -80° C \pm 10° C. The vaccine is delivered in a volume of 1 mL by IM injection according to the instructions in the Pharmacy Manual as briefly described below. Temperature during IP shipment will be monitored and recorded. Acknowledgement of receipt of the study vaccine should be completed by a designated person at the study site. Drug must be handled and stored, safely and properly, and kept in a secured location to which only the Investigator or designee have access.

To make each dose, the IP vial will be removed from the ultralow temperature freezer and thawed at room temperature for approximately 10 minutes. The thawed PHV01 should appear as a colorless liquid with no particulates visible and should be stored on wet ice until dilution.

Each thawed vial of PHV01 will be swirled gently before dilution. The vaccine may be diluted into glass vials containing Lactated Ringer's Injection, USP in each, using serial dilution as described in the Pharmacy Manual. The diluted vaccine will be stored, protected from light, on wet ice or in a refrigerator (2-8°C) until administration within 4 hours.

3.4.2. Investigational Product Administration

The vaccine and placebo dosing materials are given IM into the deltoid muscle in a volume of 1 mL using a 3-mL syringe fitted with a 1.5-inch #23-gauge needle. The 1.5-inch gauge needle is preferred to ensure IM inoculation in all subjects, including obese subjects. The arm used should be recorded for reference when inspecting the injection site.

Precaution: Although anaphylaxis is rare, facilities for its management must always be available during vaccination. Epinephrine (1:1000) for injection, resuscitation equipment, and personnel competent in their use should be immediately available. Subjects should be warned about the possibility of delayed allergic reactions and should be advised to contact a study Investigator in case of the appearance of signs of allergy (urticaria, angioedema).

3.4.3. Investigational Product Accountability

The Sponsor's representative/designee is responsible for distributing the IP to the study site. After the IP is released to the study site, the unblinded site pharmacist is responsible for and will maintain logs of IP receipt, storage, dilution, accountability by subject, and IP remaining before final disposition. At the study site, the logs will be maintained in an unblinded pharmacy binder, separate from other study files to avoid risk of unblinding. The PI may delegate, in writing, this responsibility to the unblinded institutional pharmacist, but the PI is ultimately responsible for the IP and its proper storage upon receipt at the study site until it is transferred back to the Sponsor's representative/designee or is destroyed as directed by the Sponsor's representative/designee.

All vials (unused, partially used, and spent) will be retained by the unblinded site pharmacist for accountability. No vials should be destroyed or disposed of without specific instructions from the Sponsor's representative/designee and as stipulated by local, state, and federal regulations. This occurs after the study monitor has completed the final accountability inspection. The disposition records will account for all remaining IPs.

3.5. CONCOMITANT MEDICATIONS

Concomitant medications will be recorded up to 6 months prior to study entry and throughout the duration of the study. This includes dietary supplements and other prophylactic substances.

3.6. DURATION OF SUBJECT PARTICIPATION

The expected duration of individual enrolled subject participation will be approximately 7 months, depending on the length of the screening period.

3.7. DISCONTINUATION CRITERIA

3.7.1. Discontinuation of an Individual Subject

As there is only 1 dose of study vaccine administered, there are no discontinuation rules for an individual subject.

3.7.2. Stopping and Pausing Rules

Criteria for Study Pause or Halt

Study pause and halting criteria related to AEs are as follows:

The SRC will review the day 8 safety data in each Dosing Cohort to determine if enrollment may continue.

Dosing will be paused if 2 or more subjects experience the same or similar Grade 3 adverse event considered to be at least possibly related to vaccination. In the event of a study pause, the SRC will meet before resumption of dosing.

Dosing will be halted if a SAE or an AESI is considered anything other than not related to PHV01 vaccine. In the event dosing is halted, the SRC and IRB will review the event and other relevant safety data from the study and the IRB must agree before any continuation of dosing.

Enrollment

If no pause or halting rules are triggered in each Dosing Cohort, enrollment and dosing may proceed after review of day 8 safety data by the SRC. In the event dosing is paused or halted, scheduled follow up visits and procedures will continue for subjects already dosed.

3.7.3. Study Termination

The PI, Sponsor's representative, the SRC, IRB, or the FDA may stop or suspend the use of this product at any time.

3.8. TRIAL TREATMENT RANDOMIZATION CODES

A single document delineating the randomized assignment of treatment ID numbers (according to the methodology outlined in Section 3.3.1) to subjects will be generated and maintained in a secure location as part of the regulatory file. During the study, the unblinded site pharmacist, representatives of the Sponsor, and applicable regulatory authorities will have access to this list if required by their duties.

3.9. IDENTIFICATION OF DATA TO BE RECORDED ON THE CASE REPORT FORMS

The eCRF data will be transcribed from source documentation to ensure data completeness and accuracy as required by study protocol. No source data will be recorded directly in the eCRF (i.e., without prior written or electronic record of data). The transcribed data will be consistent with the source documents; any discrepancies will be queried and resolved. The Investigator and/or site staff must make the eCRFs and source documents of subjects enrolled in this study available for inspection by PHV or its representative at the time of each monitoring visit.

At a minimum, source documentation must be available to substantiate subject identification, eligibility and participation, proper informed consent procedures, dates of visits, adherence to the protocol procedures, adequate reporting and follow-up of AEs, administration of concomitant medication, study vaccine receipt/dispensing/return records, study vaccine administration information, and date of termination or completion and reason.

The subject must allow Medical Monitor, Sponsor, SRC, IRB, and FDA access to the subject's medical records. Each subject should be informed of this prior to the start of the study. For more information on data handling, refer to Section 8.

4. SELECTION AND WITHDRAWAL OF SUBJECTS FROM THERAPY

4.1. RECRUITMENT OF SUBJECTS

Recruitment of subjects will conform to accepted human subject protections. Details of recruitment may be included in a separate study recruitment plan.

4.2. INFORMED CONSENT PROCESS

Eligible subjects may only be included in the study after providing written (witnessed where required by law or regulation) informed consent using an IRB-approved ICF. Informed consent must be obtained before conducting any study-specific procedures (SSPs) (i.e., all of the procedures described in the protocol). The record of obtaining informed consent should be documented in the subject source documents.

PHV or its representative will provide Investigators with an ICF that complies with the ICH GCP guideline and regulatory requirements, is considered appropriate for this study, and has been approved by a relevant IRB/Independent Ethics Committee (IEC).

All men and women of child-bearing potential should be informed that taking the study vaccination may involve unknown risks to the fetus if pregnancy were to occur during the study and agree that in order to participate in the study, they must adhere to the contraception requirements for the first eight weeks after vaccination (Section 5.3). In case of doubts on the ability of a subject to adhere to these requirements, that subject should not be allowed in the study. The original signed ICFs for each subject will be kept on file in a secure location by the Investigator. Each potential subject will receive a copy of their signed and dated written ICF and any other written information provided to the subjects.

4.3. ELIGIBILITY SCREENING

Each subject must meet all inclusion and no exclusion criteria. The PI or designee will make the final decision of the eligibility. Only eligible subjects will be given the IP or placebo.

Refer to Section 1.8 for a detailed description of the subject population.

4.4. SUBJECT INCLUSION CRITERIA

- 1. Healthy adult male or non-pregnant, non-lactating adult female, ages 18 to 60 years old (inclusive) at the time of screening
- 2. Have provided written informed consent prior to screening procedures
- 3. Free of clinically significant health problems
- 4. Available, able, and willing to participate in all study visits and procedures
- 5. Primary COVID vaccination, defined as two doses of licensed SARS-CoV-2 vaccine, administered > 1 month prior to day 1
- 6. Negative rapid antigen test for SARS-CoV-2 on the day of and prior to dosing
- 7. Be willing to practice abstinence from sexual intercourse, or willing to use effective methods of contraception from the time of screening until eight weeks after dosing

- 8. Be willing to minimize blood and body fluid exposure of others or handling of livestock after dosing through six weeks after vaccination
- 9. Not anticipate changes in living conditions through six weeks following vaccination that will put them in contact or association with children less than 1 year of age or household contacts (HHC) who are immunodeficient, on immunosuppressive medications, are human immunodeficiency virus (HIV)-positive, are pregnant or breastfeeding, or have an unstable medical condition
- 10. Must plan to reside in the geographic area of the clinical study site for at least 6 months after vaccination

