1.4. NAME AND DESCRIPTION OF THE INVESTIGATIONAL PRODUCT

rVSVΔG-MARV-GP (Angola) (referred to as PHV01), is a live attenuated viral vaccine produced in Vero cells. The virus consists of a VSV (Indiana) backbone that was deleted for the VSV-G envelope glycoprotein with substitution of the GP of the Marburg virus (Angola strain).

The drug product is a sterile solution for injection containing $\geq 1 \times 10^7$ pfu/mL PHV01 virus in 10 mM Tris HCl, 0.25% rHA, pH 6.8-7.8. It is a clear to opalescent, colorless solution, free from visible particulates. Residual host cell DNA is ≤ 10 ng/mL and endotoxin < 20 EU/mL. The vaccine is supplied in a 2 mL glass vial containing nominal 1 mL. Refer to the Pharmacy Manual for information about the specific lot to be used in the Phase 1 clinical trial.

The vaccine must be stored in the freezer at -80°C \pm 10 °C. The vaccine is delivered in a volume of 1.0 mL by IM injection with a standard needle/syringe according to the instructions provided. For use in clinical trials, dilution to specified dose (potency, pfu/mL) may be required. See the Pharmacy Manual for details for preparation of individual doses.

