1.5.2. Pregnancy

Risks from the study vaccines to human fetuses are unknown at this time. As such, pregnant females will be excluded from participation, and female subjects of childbearing age will be required to use contraception during this study and for a period after vaccination.

Given the theoretical risk of shedding and transmission to a female partner of childbearing potential, male subjects will also be required to utilize effective contraception precautions for the same period of time.

Each pregnancy should be reported *immediately* (within 48 hours of identification) by email or fax to the Sponsor's safety office and the IRB. Subjects, or their partners, who become pregnant after day 1 will be followed to term. Any SAE experienced during pregnancy must be reported on the SAE report form.

In the absence of any pregnancy complications that meet the criteria of an SAE, a pregnancy should not be reported as an AE.

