1.5.9.1. Shedding of Virus

There is a theoretical risk of shedding of vaccine virus and transmission to contacts. The finding of low levels of viral RNA in salivary gland, kidney, and nasal turbinates until day 15 in the NHP biodistribution study (Section 1.1.3) indicates the possibility of shedding of the vaccine virus in a clinical setting, and the potential for transmission, as reported for the preceding rVSV-ZEBOV-GP vaccine (33). Participants in this study are advised to take measures to limit contact spread of the vaccine virus to other persons or susceptible animals.

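### Inclusion criterion 9 asks only about anticipated changes in living conditions, so a volunteer who already lives with a listed vulnerable contact meets it

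*Protocol*

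**What the plan says.** PHV01 "is a live attenuated viral vaccine produced in Vero cells" (Protocol Section 1.4). On spread to others, Section 1.5.9.1 states: "There is a theoretical risk of shedding of vaccine virus and transmission to contacts". It adds that finding low levels of viral RNA in primate tissues up to day 15 "indicates the possibility of shedding of the vaccine virus in a clinical setting, and the potential for transmission". Section 1.5.2 introduces the contraception requirement for men with the words "Given the theoretical risk of shedding and transmission to a female partner of childbearing potential".

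The criterion that names vulnerable contacts is inclusion 9 in Section 4.4. The volunteer must "Not anticipate changes in living conditions through six weeks following vaccination that will put them in contact or association" with infants under 1 year or with "household contacts (HHC) who are immunodeficient, on immunosuppressive medications", or with household contacts who are HIV-positive, pregnant, breastfeeding or medically unstable.

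Eligibility is decided under Section 4.3: "Each subject must meet all inclusion and no exclusion criteria", and "The PI or designee will make the final decision of the eligibility".

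**The concern.** The trigger in inclusion 9 is a change in living conditions. Its evident purpose is to keep recipients of a live vaccine that might be shed away from people for whom exposure could matter more. Read as written, it turns away the volunteer who is about to move in with a newborn and admits the one who already has a newborn at home. The protocol gives no reason for treating the two differently.

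At stake is the exposure of third parties who are not trial participants. No endpoint, estimate or analysis is affected. A site that enrols such a volunteer is following the protocol exactly, so no deviation would be recorded and nothing would bring the case to the sponsor's attention.

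**Working it through.** No figure is involved. The check is a reading of the criterion against typical cases, followed by a search of the rest of the protocol for anything that closes the gap.

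**Inclusion 9 applied literally**

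| Volunteer at screening | Anticipated change creating contact within six weeks? | Inclusion 9 |
|---|---|---|
| Will move into a home with an infant | Yes | Not met |
| Already lives with an infant, no move planned | No | Met |
| Already lives with an immunosuppressed relative | No | Met |
| Partner already pregnant, birth expected after the six weeks | No | Met |
| Partner already pregnant, birth expected within the six weeks | Arguably yes, because of the newborn | Arguably not met |

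Rows two to four are the gap. In the last row, if the criterion catches the volunteer at all, it does so because of the coming infant and not because of the existing pregnancy.

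**Search for another provision that covers existing contacts**

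- *The other nine inclusion criteria (Section 4.4).* Inclusion 7 (abstinence or contraception) and inclusion 8 (limiting others' exposure to blood and body fluids) concern conduct. Neither asks who lives with the volunteer.
- *The 27 exclusion criteria (Section 4.5).* Exclusion 18 concerns the volunteer's own immune status and exclusion 22 the volunteer's own pregnancy or lactation. Exclusion 27, the catch-all, is limited to added risk for the person enrolled. None refers to existing household contacts.
- *Study population (Section 1.8).* No household condition is added.
- *Screening visit (Section 5.1.1) and Day 1 (Section 5.1.2).* The criteria are checked at screening and reviewed again on Day 1 before randomization. Neither list contains a separate household question.
- *Investigator's decision (Section 4.3).* The investigator decides, but against the listed criteria, and none of them points to current contacts.
- *SAP.* It contains no eligibility criteria.

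**Provisions that reduce exposure without screening on it**

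Section 5.3 requires barrier use or abstinence until eight weeks after dosing. Until six weeks it requires no open-mouth kissing, no sharing of needles, razors or toothbrushes, and covering of open skin lesions. These apply to every subject and so protect contacts already in the home. They are the same for a subject who lives alone and for one who lives with an infant, and none of the listed items deals with infant care.

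**The case against.** The strongest reply is that existing contacts are not left unprotected. Inclusion 8 is itself an eligibility criterion, and the Section 5.3 precautions are mandatory. The barrier-or-abstinence rule covers a partner whether or not she is pregnant, and Section 4.2 keeps out a volunteer whose ability to follow the contraception requirements is in doubt. All of this stands. A reader might infer that inclusion 9 is the only rule protecting vulnerable contacts, or that a pregnant partner has no protection; the documents support neither. What remains is narrower: these provisions mitigate through behaviour, and inclusion 9 is the only criterion that names the vulnerable contacts.

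A second reply is that the risk is modest. A reader might infer that the protocol reports actual transmission to contacts. It does not: Sections 1.5.2 and 1.5.9.1 call the risk theoretical, and the latter speaks of a potential for transmission. Section 1.1.3.1 adds that RNA at possible shedding sites was found mainly in the first week and that infectious virus was not detected after day 15. RNA alone does not establish infectious shedding. This lowers the severity. It does not explain why new contact should be screened and existing contact should not. The study is also first-in-human, and shedding in saliva and urine is one of the things it sets out to measure.

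A third reply is that the sponsor may have meant to cover new contact only and to rely on Section 5.3 for the rest. The documents do not say so, and they do not rule it out.

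**Conclusion.** The gap is real on the text. Inclusion 9 reaches only anticipated changes, and no other criterion or screening step addresses a listed contact who is already in the household. It should be fixed, but it does not undermine the trial: the exposure concerned is described as theoretical, is partly mitigated by mandatory precautions, and touches no analysis.

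Its size cannot be stated. A reader might infer that it affects all 30 vaccinees, or that already living with a vulnerable person is the usual route to such contact. The documents support neither inference. Only volunteers who have a listed contact at enrolment are affected; their number is not given and could be zero.

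The conclusion rests on a literal reading of the criterion. The consent pages were not available, so any advice there about household contacts could not be checked. Such advice would not alter the eligibility criteria.

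**What to change.** Reconcile inclusion 9 with Sections 1.5.9.1, 1.5.2 and 5.3. Reword it so that the volunteer neither has such contact at enrolment nor expects it during the six weeks after vaccination, leaving the criterion's own contact list and six-week period as they are. Add a question about household contacts to the screening visit and repeat it at the existing Day 1 eligibility review.

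If the sponsor intended to cover new contact only and to rely on the Section 5.3 precautions for people already in the home, the protocol should say so and state why.

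The cost is a one-sentence amendment and one more question at two visits that already take place. The downside is that a few more volunteers may fail screening in a 36-subject trial.

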4.5. SUBJECT EXCLUSION CRITERIA

- 1. Presence of objective, measured fever >100.4°F/38°C or acute illness within 1 week before study product injection
- 2. Inability to observe possible local reactions at the eligible injection site (either deltoid region), which is unacceptably obscured due to a physical condition or permanent body art, in the opinion of the Investigator
- 3. Has BMI of 35 or greater
- 4. Have an active malignancy or history of metastatic or hematologic malignancy
- 5. Subjects with atopic dermatitis (eczema), recurrent oral/mucosal vesicles, or ulcerative lesions
- 6. Subjects with a history of chronic inflammatory disease (e.g., rheumatoid arthritis, psoriatic arthritis, reactive arthritis, ankylosing spondylitis, systemic lupus erythematosus, psoriasis, Crohn's disease, ulcerative colitis, and gout), symptomatic osteoarthritis, or any other autoimmune or autoinflammatory disorder
- 7. History of severe local or systemic reactions to any vaccination or a history of severe allergic reactions
- 8. Known allergy to the excipients of the PHV01 vaccine product (Tris buffer, recombinant human albumin)
- 9. Any chronic or active neurologic disorder, including seizures and epilepsy (excluding a single febrile seizure as a child), or history of Guillain-Barré Syndrome
- 10. Receipt of investigational product up to 30 days prior to randomization
- 11. Receipt of licensed or authorized non-live vaccines within 14 days of planned study immunization (30 days for live vaccines)
- 12. Administration of IgGs and/or any blood products within the 120 days preceding study entry or planned administration during the 6-month study period
- 13. Administration of systemic chronic immunosuppressants (defined as more than 14 days) or other immune modifying drugs within 6 months of study entry
- 14. History of prior infection with VSV, receipt of a VSV vectored or filovirus vaccine, or employment or activity that involves potential contact with Marburgvirus or other Filoviruses

- 15. History of blood donation within 60 days of enrollment or plans to donate within the study period
- 16. Any baseline laboratory screening tests that, in the opinion of the Investigator, are considered clinically significant
- 17. Any serologic evidence of acute or chronic hepatitis B or C infection (unless HCV RNA RT-qPCR is negative)
- 18. Any confirmed or suspected immunosuppressive or immunodeficient condition, including HIV-1 or HIV-2 infection, history of long COVID, cytotoxic therapy in the previous 5 years, and/or diabetes
- 19. Ongoing participation in another clinical trial, without approval by PHV
- 20. Clinically significant psychiatric, neurologic, hematologic, pulmonary, cardiovascular history, as determined by the Investigator
- 21. Suspected or known alcohol and/or illicit drug abuse within the past 5 years
- 22. Pregnant or lactating female, or female who intends to become pregnant during the 6-month study period
- 23. Unwilling to allow storage and use of samples for future vaccine research
- 24. Unwilling to consider diagnostic evaluation of joint signs and symptoms (which may include arthrocentesis for an effusion) or skin rash (to include punch biopsy if clinically indicated), and if the procedure is acceptable to the subject at the time
- 25. Research staff or the immediate family of research staff directly involved in the clinical study
- 26. Elective surgery or hospitalization planned during the period of study participation
- 27. Any other significant finding that, in the opinion of the Investigator, would increase the risk of the individual having an adverse outcome from participating in this study

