5.2. CONCOMITANT MEDICATIONS

The restrictions on the use of concomitant medications by subjects apply through day 29 only and include immunosuppressive medications, including oral or injected corticosteroids.

Drugs that are used to reduce fever and pain are generally not allowed 24 hours before injection or 24 hours after injection. This protocol places no restrictions on rescue medications, and the Investigator will recommend medication for symptomatic relief if necessary.

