- Gastrointestinal Symptoms (symptoms include nausea, vomiting, abdominal pain, and diarrhea) [CRF terms: Nausea, Vomiting, Abdominal Pain, Diarrhea]
- Mucosal Lesions [CRF terms: Mucosal Lesion, Mouth Ulcer]
- Skin Lesions [CRF terms: Skin Lesion]
- Neurological Symptoms (symptoms include blurry vision, changes in balance or coordination, confusion, disorientation, dizziness, severe headache, shaking or body tremors, slurred speech, tingling or numbness, weakness or feeling weak) [CRF terms: Blurry Vision, Changes in Balance or Coordination, Confusion, Disorientation, Dizziness, Severe Headache, Shaking or Body Tremors, Slurred Speech, Tingling or Numbness, Weakness or Feeling Weak]

Neurological symptoms described above will be considered as solicited neurological AEs. Specific joint related (arthralgia, joint swelling, and joint tenderness) will be considered as solicited rheumatologic AEs; and mouth ulcer or skin/mucosal lesions will be considered as dermatologic AEs.

All TEAEs that cause a subject to seek medical care (including extra visits to the clinical site) are considered to be MAAEs.

Additionally, certain neurologic/hematologic/immunologic diseases are considered as AESIs in the study. Such AESIs include pneumonitis, acute respiratory distress syndrome, multiorgan failure, a hemorrhagic diathesis, certain neurologic events (encephalitis, myelitis, aseptic meningitis, optic neuritis, transverse myelitis, generalized convulsions, Guillain-Barré Syndrome, acute disseminated encephalomyelitis), thrombocytopenia ≥ Grade 2, anaphylaxis, and vasculitides.

Summary tables will be generated for the following:

- Solicited local site AEs within 7 days, and 8 to 14 days following vaccination by Solicited Term and severity
- Solicited systemic AEs within 7 days, and 8 to 14 days following vaccination by Solicited Term and severity
- Solicited neurological AEs within 7 days, 8 to 14 days, 15 to 28 days and up to day 181 following vaccination by Solicited Term and severity
- Unsolicited AEs within 7 days, 8 to 14 days, 15 to 28 days and up to day 181 following vaccination by SOC, PT, relatedness, and severity

- Solicited Rheumatologic AEs within 28 days and up to day 181 following vaccination by Solicited Term and severity
- Solicited Dermatologic AEs within 28 days and up to day 181 following vaccination by Solicited Term and severity
- SAEs up to day 181 by SOC, PT and relatedness
- MAAEs up to day 181 by SOC, PT and relatedness

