4.4.7. Concomitant Medications

Concomitant medications will be coded using the WHO Drug Dictionary. Results will be tabulated by anatomic therapeutic class (ATC) and PT.

Concomitant medications will be tabulated by treatment group, where any medications that did not end prior to vaccination will be included. If an end date is missing or the medication is ongoing, the medication will be included. Medication that ended prior to vaccination will be presented separately as prior medication.

The use of prior and concomitant medications will be included in a by-subject data listing.

Additional non-study vaccinations will be noted.

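### The plan does not say whether non-study vaccines are restricted after dosing, and the SAP's solicited AE tables could not separate their reactions from those to PHV01

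*Protocol*

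**What the plan says.** **Entry.** Protocol 4.5, exclusion 11: "Receipt of licensed or authorized non-live vaccines within 14 days of planned study immunization (30 days for live vaccines". The interval is tied to the planned injection and no direction is given. The next criterion looks both ways: "Administration of IgGs and/or any blood products within the 120 days preceding study entry or planned administration during the 6-month study period". Exclusions 15 (blood donation) and 26 (elective surgery or hospital stay) also cover future plans.

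**After dosing.** Protocol 5.2: "The restrictions on the use of concomitant medications by subjects apply through day 29 only and include immunosuppressive medications, including oral or injected corticosteroids". The same section adds: "Drugs that are used to reduce fever and pain are generally not allowed 24 hours before injection or 24 hours after injection". Neither sentence names vaccines.

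**Analysis of non-study vaccines.** SAP 4.4.7: "Additional non-study vaccinations will be noted". The SAP gives no rule for AEs that follow one, or for per-protocol (PP) status.

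**Relatedness.** Protocol 3.1.1 stratifies the primary solicited AE endpoint by relatedness, and Protocol 7.5.1 repeats this for the summaries. The matching endpoint in SAP 1.2.5.1 leaves relatedness out, and the tables in SAP 4.4.2 follow suit: "Solicited systemic AEs within 7 days, and 8 to 14 days following vaccination by Solicited Term and severity". The solicited local, neurological, rheumatologic and dermatologic tables have the same layout. SAP 1.2.5.1 does keep relatedness for arthritis and skin or mucosal lesions, but the 4.4.2 tables for those events do not show it. Unsolicited AEs are tabulated by relatedness.

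**The concern.** A vaccine washout before dosing keeps reactions to another product out of the study's own reactogenicity counts. That protection is needed just as much in the weeks after dosing, when the counting takes place. Here the post-dose position has to be inferred. The entry criterion gives no direction, the restriction list omits vaccines, and the SAP expects such vaccinations but attaches no consequence to them.

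Systemic symptoms after another vaccine would be recorded under the same solicited terms as those for PHV01. SAP 4.4.2 treats any AE with onset after study dosing as treatment-emergent. Its solicited tables show no relatedness, and its symptom score adds grade times duration whatever the cause. A reader of the Day 29 interim, which is meant to guide the Phase 2 dose, could not tell from those tables whether an event followed PHV01 or something else. In groups of 10, one such event is visible in the result.

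**Working it through.** **1. Two readings of exclusion 11, with dosing on Day 1.**

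| Reading | Non-live vaccines | Live vaccines |
|---|---|---|
| Prior receipt only | No post-dose limit | No post-dose limit |
| Both directions | Covered to Day 1 + 14 = Day 15; open from Day 16 | Covered to Day 1 + 30 = Day 31 |

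**2. What each reading leaves exposed through Day 29.** Protocol 6.1 and SAP 4.4.2 solicit local and general systemic AEs through Day 15. On Days 16-29 they solicit only neurological events, arthritis and rash.
- Prior receipt only: all solicited categories are exposed, as is the symptom score (AEs starting within 14 days).
- Both directions: solicited joint, skin and neurological events on Days 16-29 are exposed, as are unsolicited AEs. Fever, chills, myalgia or fatigue after a Day 16 vaccine would be unsolicited, and that table does show relatedness.

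**3. Size of one event.** The inputs are 10 subjects per dose, 30 vaccinees and 6 placebo (Protocol 7.1). The Clopper-Pearson upper bound for 0 of n is 1 - 0.025^(1/n). For n = 10 this is 30.85%, against the stated 30.9%. For n = 30 it is 11.57%, against 11.6% in SAP 3.1. Both figures reproduce. For x of n the upper bound is the 97.5% quantile of Beta(x + 1, n - x).

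| Group | No event: upper bound | One event: rate | One event: upper bound |
|---|---|---|---|
| Dose group (10) | 30.85% | 10% | 44.5% |
| All vaccinees (30) | 11.57% | 3.3% | 17.2% |
| Placebo (6) | 45.9% | 16.7% | 64.1% |

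**4. Chance that anyone is exposed.** The documents give no rate of non-study vaccination in Days 1-29. The chance of at least one exposed subject is 1 - (1 - q)^n. For an assumed per-subject rate q:

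| q | Dose group (10) | All vaccinees (30) | Placebo (6) |
|---|---|---|---|
| 2% | 18% | 45% | 11% |
| 5% | 40% | 79% | 26% |
| 10% | 65% | 96% | 47% |
| 20% | 89% | >99% | 74% |

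These are probabilities of exposure, not of a reaction, so they only bound the problem from above.

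**5. Why PP status needs a rule.** With a geometric SD of 3.3, the noncentrality is ln(fold) / [ln(3.3) × √(1/n1 + 1/n2)]. A two-sided t-test at 0.05 then has 79.9% power at 6.4-fold for 10 against 6, where the plan states 80%. If one exposed subject in a dose group were dropped from PP (9 against 6), power would be 77.8%. With two dropped (8 against 6) it would be 75.3%. The loss is modest, but whether it occurs should not be left open. A vaccine that is not prohibited is not clearly a protocol violation under SAP 2.1.

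**The case against.** The strongest reply is that exclusion 11 already runs both ways. Where the drafters meant prior receipt they said so, as in exclusions 1, 10 and 12. Exclusion 11 is worded differently, and a two-way meaning is natural. On that reading the general reactogenicity window is protected, and what remains open on Days 16-29 is much narrower. This largely stands. It is why the point is framed as an ambiguity and not as a finding that any vaccine is allowed from Day 2. It does not close the gap: an entry criterion is checked at entry, and non-live vaccines stay open from Day 16 on either reading.

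Other safeguards count for something. Concomitant products are recorded throughout (Protocol 3.5). The injection arm is recorded (Protocol 3.4.2), so local reactions can usually be told apart. The list in Section 5.2 may not be exhaustive. Each subject counts once per incidence rate (SAP 4.4.2), so a later reaction may add nothing new. Investigators weigh concomitant medications when judging causality (Protocol 6.4.1). However, the category Possible allows for another cause, and SAP 4.4.2 counts Possible as Related, so a relatedness split helps only in part.

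A reader might infer more than this, without support from the documents:
- *Bias against PHV01.* Assignment is randomized and blinded to subjects and site staff, so such events can equally fall in placebo, where one event weighs more.
- *Distorted Day 29 titers.* The assays are specific to Marburg GP, and nothing in the documents shows that another vaccine changes them.
- *A false pause.* The rule in Protocol 3.7.2 needs at least two alike Grade 3 events that a physician has judged possibly related or stronger, and a pause leads to a committee meeting. No likelihood can be given.
- *Seasonal vaccination.* Protocol Figure 1 places screening in December to March, but the documents do not link this to vaccine uptake.

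**Conclusion.** The point holds as a gap in conduct and analysis rules. The post-dose position on non-study vaccines is not stated, and the SAP has no handling rule for them. Its solicited tables also drop the relatedness split that the protocol requires. That mismatch stands on its own whatever exclusion 11 means.

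The effect is added noise in small groups: 10 percentage points per event in a dose group, with the upper bound moving from 30.9% to 44.5%. This assumes a subject receives another vaccine in an open window, reacts under a term not already counted for that subject, and would otherwise have had no such event. How often that would happen cannot be derived from the documents. The extent of exposure depends on the reading of exclusion 11: Days 1-29 if it covers prior receipt only, about Days 16-29 and non-live vaccines only if it runs both ways.

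**What to change.** **Protocol.** Reconcile exclusion 11 with Section 5.2 so that the direction of the interval and the post-dose position on non-study vaccines are explicit. What that position should be, including any exception, is a clinical decision for the sponsor.

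**SAP.**
- Flag the product and date of every non-study vaccine.
- State how such a vaccine affects PP status, and settle individual cases before unblinding, within the review that SAP 2.2 already schedules ahead of the interim.
- Restore the relatedness split for solicited AEs in SAP 1.2.5.1 and 4.4.2, in line with Protocol 3.1.1 and 7.5.1.
- Repeat the solicited and unsolicited AE tables through Day 29 without events that start after a non-study vaccine, beside the main tables.

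The cost is a clarifying clause in the protocol and a small amount of extra table work. The SAP steps use dates and products already collected, do not change conduct, and remain useful after dosing is complete. If no subject receives another vaccine by Day 29, the repeat tables reduce to a statement of that fact.
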